Assessment of immature platelets was introduced as a non-invasive test of real time thrombopoiesis. They are newly released in the circulation with a larger size & greater RNA content than mature platelets, and can be measured by automated hematology analyzer equipped with reticulocyte detection channel and described as immature platelet fraction (IPF-%) and absolute immature platelet count (A-IPC). A high IPF-% has been suggested as an indicator of thrombocytopenia due to rapid platelet consumption, while a low IPF-% is characteristic of bone marrow suppression states. IPF-%/A-IPC has the competency to be performed routinely and, therefore, can provide therapeutic and diagnostic feedback in the compatible life threatening conditions (**Hong et al., 2013**).

Aim of work

The aim of this work is to show the utility of estimating IPF-% and A-IPC using a reticulocyte detection channel CBC auto analyzer as a simple reproducible blood analysis to be employed in the differential diagnosis of pregnancy-associated thrombotic microangiopathic conditions.

Patients and Methods

This study aiming to show the utility of estimating IPF-% and A-IPC using a reticulocyte detection channel CBC auto analyzer as a simple reproducible blood analysis to be employed in the differential diagnosis of pregnancy-associated thrombotic microangiopathic conditions. Patients were recruited from Ain Shams University Maternity Hospital.

Study sample was 57 women and were classified into three groups:

Group 1: *SPE/HELLP group.* This group will include 24 pregnant women (gestational age of >20 weeks) who are diagnosed as having TMA with provisional diagnosis of pre-eclampsia, HELLP syndrome.

Group 2: *TTP/HUS group.* This group will include 13 pregnant women (gestational age of >20 weeks) who are diagnosed as having TMA with provisional diagnosis of TTP/HUS.

Group 3: *Control group.* This group will include 20 pregnant women (gestational age of >20 weeks) having normal pregnancy with normal blood pressure and platelet count.

Inclusion criteria

Women will be included if they are:

- Older than 20 years of age
- Pregnant with singleton intrauterine pregnancy
- More than 20 weeks of gestation

Exclusion criteria

Patients will be excluded from the study if there was any of the following:

- Congenital malformation and fetuses with chromosomal or genetic syndrome.

- Recent blood transfusion.
- Refusal to participate in the study.
- BMI <18.

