- **(ROC) curve analysis for discrimination between patients with TTP/HUS or SPE/HELLP using the IPF-%:** The optimal cutoff values for IPF-% for discrimination between patients with TTP/HUS or SPE/HELLP was >15.9 %. The sensitivity and specificity were 76.92% and 66.7%, respectively. The positive predictive value (PPV) and negative predictive value (NPV) were 55.6 % and 84.2%, respectively (AUC=0.692) (**Table 18**) (**Figure 23**).

Assessment of Immature Platelet Fraction in Pregnancy-Associated Thrombotic Microangiopathy: (Results)

[figure not shown]

Figure (23): Receiver-operating characteristic (ROC) curve analysis for discrimination between patients with TTP/HUS or SPE/HELLP using the IPF.

Assessment of Immature Platelet Fraction in Pregnancy-Associated Thrombotic Microangiopathy: (Results)

- **(ROC) curve analysis for discrimination between patients with TTP/HUS or SPE/HELLP using the schistocyte count:** The optimal cutoff values for schistocyte count for discrimination between patients with TTP/HUS or SPE/HELLP was $>4.6\%$. The sensitivity and specificity were 61.54% and 91.67% , respectively. The positive predictive value (PPV) and negative predictive value (NPV) were 80% and 81.5% , respectively (AUC=0.771) (Table 19), (Figure 24).

[figure not shown]

Figure (24): Receiver-operating characteristic (ROC) curve analysis for discrimination between patients with TTP/HUS or SPE/HELLP using the schistocyte count.

Comparison of the receiver-operating characteristic (ROC) curves:

Comparison of the receiver-operating characteristic (ROC) curves between IPF-% or schistocyte count revealed no significant difference between IPF-% and schistocyte count regarding discrimination between patients with TTP/HUS or SPE/HELLP (P-value >0.05) (Table 19), (Figure 25).

Assessment of Immature Platelet Fraction in Pregnancy-Associated Thrombotic Microangiopathy: (Results)

Table (19): Comparison of ROC curves for discrimination between patients with TTP/HUS or SPE/HELLP using the IPF or schistocyte count

Index	IPF	Schistocyte count	Difference	z	P-value¶
Area under ROC (AUC)	0.692 (0.519 to 0.833)	0.771 (0.603 to 0.893)	0.079 (-0.171 to 0.328)	0.617	0.537

Diagnostic indices are presented as value (95% CI).

¶DeLong method.

Assessment of Immature Platelet Fraction in Pregnancy-Associated Thrombotic Microangiopathy: (Results)

[figure not shown]

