Figure (25): Comparison of ROC curves for discrimination between patients with TTP/HUS or SPE/HELLP using the IPF or schistocyte count.

Assessment of Immature Platelet Fraction in Pregnancy-Associated Thrombotic Microangiopathy: (Results)

Table (20): ROC curve analysis for discrimination between patients with TMA and normal controls using the IPF-%s or schistocyte count

Index	IPF-%	Schistocyte count
Positive group (TMA)	37 (64.9%)	37 (64.9%)
Negative group (normal controls)	20 (35.1%)	20 (35.1%)
Area under the ROC curve (AUC)	0.820 (0.695 to 0.909)	0.838 (0.716 to 0.922)
z statistic	5.678	8.660
P-value	<0.0001¶	<0.0001¶
Associated cut-off criterion	>8.1 %	>0 %
Sensitivity (%)	86.49 (71.2 - 95.5)	67.57 (50.2 - 82.0)
Specificity (%)	65.00 (40.8 - 84.6)	100.00 (83.2 - 100.0)
Positive predictive value (PPV, %)	82.1 (66.5 - 92.5)	100.0 (86.3 - 100.0)
Negative predictive value (NPV, %)	72.2 (46.5 - 90.3)	62.5 (43.7 - 78.9)

Diagnostic indices are presented as value (95% CI).

¶DeLong method.

- **(ROC) curve analysis for discrimination between patients with TMA or control using the IPF-%:** The optimal cutoff values for IPF-% for discrimination between patients with TMA or control was >8.1%. The sensitivity and specificity were 86.49% and 65%, respectively. The positive predictive value (PPV) and negative predictive value (NPV) were 82.1 % and 72.2%, respectively (**Table 20**), (**Figure 26**).

Assessment of Immature Platelet Fraction in Pregnancy-Associated Thrombotic Microangiopathy: (Results)

[figure not shown]

Figure (26): ROC curve for discrimination between patients with TMA and normal controls using the IPF.

- **(ROC) curve analysis for discrimination between patients with TMA or control using schistocyte count:** The optimal cutoff values for schistocyte count for discrimination between patients with TMA and normal controls was >0 %. The sensitivity and specificity were 67.57 % and 100%, respectively. The PPV and NPV were 100 % and 62.5%, respectively (**Table 20**), (**Figure 27**).

Assessment of Immature Platelet Fraction in Pregnancy-Associated Thrombotic Microangiopathy: (Results)

[figure not shown]

Figure (27): ROC curve for discrimination between patients with TMA and normal controls using the schistocyte count.

- **Comparison of the receiver-operating characteristic (ROC) curves:**

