Variable	Regression coefficient (B)	SE for B	Wald	P-value	Odds ratio (OR)	95% CI for OR
IPF (%)	0.104	0.048	4.666	0.031	1.110	1.010 to 1.220
Schistocyte count (%)	0.107	0.046	5.283	0.022	1.113	1.016 to 1.219
Constant	-3.251					

Assessment of Immature Platelet Fraction in Pregnancy-Associated Thrombotic Microangiopathy: (Results)

Table (24): Receiver-operating characteristic (ROC) curve derived from the multivariable binary logistic regression model for discrimination between patients with TTP/HUS or SPE/HELLP using the IPF-% and schistocyte count combined

Sample size	37
Positive group (TTP/HUS)	13 (35.1%)
Negative group (SPE/HELLP)	24 (64.9%)
Disease prevalence (%)	35.1
<hr/>	
Index	Value
Area under the ROC curve (AUC)	0.827 (0.667 to 0.931)
z statistic	4.385
P-value	<0.0001
Sensitivity (%)	92.3 (64.0 - 99.8)
Specificity (%)	62.5 (40.6 - 81.2)
Positive likelihood ratio (+LR)	2.46 (1.4 - 4.2)
Positive likelihood ratio (-LR)	0.12 (0.02 - 0.8)
PPV, %	57.1 (34.0 - 78.2)
NPV, %	93.7 (69.8 - 99.8)

Diagnostic indices are presented as value (95% CI).

¶DeLong method.

Assessment of Immature Platelet Fraction in Pregnancy-Associated Thrombotic Microangiopathy: (Results)

[figure not shown]

Figure (30): Discrimination between patients with TTP/HUS or SPE/HELLP using IPF-% and schistocyte count combined.

Table 24 and Figure 30 shows the results of ROC curve analysis derived from the predicted probabilities as estimated from the multivariable binary logistic regression model for discrimination between patients with TTP/HUS or SPE/HELLP using the IPF and schistocyte count combined.

Table (25): Comparison of the receiver-operating characteristic (ROC) curves for discrimination between patients with TTP/HUS or SPE/HELLP using the IPF, schistocyte count, or IPF and schistocyte count combined

Marker	AUC	95% CI
IPF-%	0.692	0.519 to 0.833
Schistocyte count	0.771	0.603 to 0.893

Assessment of Immature Platelet Fraction in Pregnancy-Associated Thrombotic Microangiopathy: (Results)

IPF-% and schistocyte count combined 0.827 0.667 to 0.931

Marker	Difference between AUCs	95% CI	Z statistic	p-value
IPF-% vs. Schistocyte count	0.079	-0.171 to 0.328	0.617	0.537
IPF-% vs. IPF and Schistocyte count combined	0.135	-0.034 to 0.303	1.569	0.117
Schistocyte count vs. IPF-% and schistocyte count combined	0.056	-0.085 to 0.197	0.780	0.435

[figure not shown]

Figure (31): Discrimination between patients with TTP/HUS or SPE/HELLP.

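### PPV and NPV for TMA against normal controls (SAP Table 20) are fixed by how many healthy women were recruited; likelihood ratios should replace them

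*SAP*

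**What the plan says.** The Protocol (Patients and Methods) gives a total and three group sizes. "Study sample was 57 women and were classified into three groups": 24 with SPE/HELLP ("This group will include 24 pregnant women (gestational age of >20 weeks"), 13 with TTP/HUS ("This group will include 13 pregnant women (gestational age of >20 weeks") and 20 controls ("This group will include 20 pregnant women (gestational age of >20 weeks"). Controls are defined as "having normal pregnancy with normal blood pressure and platelet count". The Protocol's statistical methods do not mention ROC analysis or predictive values.

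The SAP prints PPV and NPV with 95% intervals for two contrasts:

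- **TMA against normal controls** (Table 20, duplicated in Table 9). For IPF-% above 8.1%: "The positive predictive value (PPV) and negative predictive value (NPV) were 82.1 % and 72.2%, respectively". The positive group is 37 of 57, or 64.9%.
- **TTP/HUS against SPE/HELLP** (Table 18, duplicated in Table 7, and Table 24). For IPF-% above 15.9%: "The positive predictive value (PPV) and negative predictive value (NPV) were 55.6 % and 84.2%, respectively". The positive group is 13 of 37, or 35.1%. Table 24 prints that share in a row labelled "Disease prevalence".

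Table 24 also gives likelihood ratios; Tables 18 and 20 do not. No external prevalence, reweighting or caution about case mix appears in either document.

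**The concern.** Sensitivity and specificity are each calculated within one disease group, so the ratio of cases to non-cases does not enter them. PPV and NPV pool the groups, so it does. When the negatives are healthy volunteers added in a number the investigators choose, the predictive values inherit that choice. An exact binomial interval around them covers sampling error at that ratio only.

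A reader of the Table 20 text could take 82.1% as the chance that a pregnant woman with IPF-% above 8.1% has TMA. The design cannot give that probability.

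**Working it through.** **1. Inputs.** Group sizes 37 TMA (24 + 13) and 20 controls. From Table 20, IPF-% above 8.1% has sensitivity 86.49% = 32/37 and specificity 65.00% = 13/20. So TP = 32, FN = 5, TN = 13, FP = 7.

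**2. Reproduce the printed figures.** PPV = TP/(TP + FP) = 32/39 = 82.1%, Clopper-Pearson 66.5 to 92.5. NPV = TN/(TN + FN) = 13/18 = 72.2%, 46.5 to 90.3. Both match the print. The other rules also match as raw proportions:

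| Rule | PPV | NPV |
|---|---|---|
| Table 20, schistocytes >0% | 25/25 = 100% | 20/32 = 62.5% |
| Table 18, IPF >15.9% | 10/18 = 55.6% | 16/19 = 84.2% |
| Table 18, schistocytes >4.6% | 8/10 = 80.0% | 22/27 = 81.5% |
| Table 24, combined | 12/21 = 57.1% | 15/16 = 93.75% (printed 93.7) |

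The arithmetic is correct. The case share built into it is 37/57 or 13/37.

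**3. Change only the number of controls in Table 20.** With 40 controls at specificity 65%, TN = 26 and FP = 14. PPV = 32/(32 + 14) = 32/46 = 69.6%. NPV = 26/(26 + 5) = 26/31 = 83.9%. The test itself has not changed.

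**4. Change the prevalence.** The documents give no clinical prevalence, so every p below is an assumption. PPV = p·Se/[p·Se + (1−p)(1−Sp)]; NPV = (1−p)·Sp/[(1−p)·Sp + p(1−Se)]. At p = 10%: PPV = 0.0865/(0.0865 + 0.3150) = 21.5%; NPV = 0.5850/(0.5850 + 0.0135) = 97.7%.

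| p | PPV, IPF >8.1% | NPV, IPF >8.1% |
|---|---|---|
| 5% | 11.5% | 98.9% |
| 10% | 21.5% | 97.7% |
| 20% | 38.2% | 95.1% |
| 50% | 71.2% | 82.8% |
| 37/57 (64.9%) | 82.1% | 72.2% |
| 80% | 90.8% | 54.6% |

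**5. Quantities that do not depend on the ratio.** LR+ = Se/(1−Sp) and LR- = (1−Se)/Sp. Intervals are on the log scale: SE(ln LR+) = √(1/TP − 1/P + 1/FP − 1/N) and SE(ln LR-) = √(1/FN − 1/P + 1/TN − 1/N), where P and N are the group sizes. As a check, Table 24's counts give 2.46 (1.43 to 4.22) and 0.12 (0.02 to 0.83), in line with its printed 1.4 to 4.2 and 0.02 to 0.8.

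| Rule | LR+ (95% CI) | LR- (95% CI) |
|---|---|---|
| IPF >8.1%, TMA vs control | 2.47 (1.34 to 4.55) | 0.21 (0.09 to 0.50) |
| IPF >15.9%, TTP/HUS vs SPE/HELLP | 2.31 (1.22 to 4.37) | 0.35 (0.12 to 0.97) |
| Schistocytes >4.6%, TTP/HUS vs SPE/HELLP | 7.38 (1.83 to 29.79) | 0.42 (0.21 to 0.84) |

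For schistocytes above 0% against controls, FP = 0, so LR+ has no finite estimate; LR- = (12/37)/1 = 0.32.

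**6. The schistocyte PPV of 100%.** This follows from an observed specificity of 20/20 and is the same at any nonzero prevalence. Its interval (86.3 to 100) is not so protected. At the lower specificity limit of 83.2% and an assumed 10% prevalence, PPV = 0.0676/(0.0676 + 0.1512) = 30.9%.

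**7. TTP/HUS against SPE/HELLP, on both sides of 35.1%.** For IPF-% above 15.9%, PPV/NPV are 20.4/96.3% at 10%, 49.7/87.1% at 30% and 69.8/74.3% at 50%. The printed 55.6/84.2% lies inside that range.

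**The case against.** The strongest reply is that the contrast serving the study's aim, differential diagnosis among TMA conditions, is TTP/HUS against SPE/HELLP, and that controls do not enter it. Doubling the controls would leave Tables 18 and 24 untouched. The Protocol describes 57 women classified into groups, partly in the past tense, and gives no quota or sample-size calculation. The 13 and 24 could be the women who presented, in which case 35.1% might approximate this hospital's mix. This stands.

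Four stronger readings are therefore not supported:

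- **That every predictive value in the SAP is clinically meaningless.** This is unproven for Tables 18 and 24.
- **That the SAP presents both shares as a prevalence.** Only the 35.1% in Table 24 carries that label. The 64.9% is shown simply as the positive group.
- **That PPV and NPV underpin the SAP's description of the combined model as predicting well.** That statement is tied to the AUC of 0.827, which does not depend on case mix. The predictive values merely follow it.
- **That correction makes everything look worse.** Below the sample share PPV falls (except the 100%) but NPV rises.

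It can also be said that the group shares, sensitivity and specificity are printed, so a reader can rescale. That is true, but the Table 20 text states the two percentages with no caution.

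**Conclusion.** The point is firm for TMA against normal controls. PPV 82.1% and NPV 72.2%, with their intervals, are set by the choice of 20 healthy controls. They become 69.6% and 83.9% with 40, and 21.5% and 97.7% at an assumed 10% prevalence. The first comparison rests only on sensitivity and specificity staying as observed; the second also rests on the assumed prevalence.

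For TTP/HUS against SPE/HELLP the conclusion is limited: the documents do not show that 35.1% is a clinical prevalence, and do not show that it is not close to one.

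This is a fault in what is reported and how it can be read, not in the calculation. Likelihood ratios remove the dependence on case share. They do not remove the effect of comparing cases with women selected for normal blood pressure and platelets, nor that of choosing cut-offs on the same data; both are separate matters.

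**What to change.** **Table 20, Table 9 and the accompanying text.** Remove PPV, NPV and their intervals for both markers. Keep sensitivity and specificity, and add the likelihood ratios with 95% CI from step 5. For schistocytes above 0%, state that LR+ is not estimable because no control was positive.

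**Table 18 (and Table 7).** Add LR+ and LR- with 95% CI for both markers.

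**Table 24.** Relabel the prevalence row as the sample case share; keep the figure, since it discloses the basis of the calculation.

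**PPV and NPV for TTP/HUS against SPE/HELLP.** Either document that the 37 women were enrolled consecutively, or show the values over a stated assumed range on both sides of 35.1%, for example 10%, 30% and 50%.

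The cost is edits to tables and text, with no new data. Some PPVs will look less favourable and some NPVs more so.

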Figure (12): Receiver-operating characteristic (ROC) curve for discrimination between patients with TMA and normal controls using the IPF.

Assessment of Immature Platelet Fraction in Pregnancy-Associated Thrombotic Microangiopathy: (Results)

[figure not shown]

Figure (13): Receiver-operating characteristic (ROC) curve for discrimination between patients with TMA and normal controls using the schistocyte count.

Assessment of Immature Platelet Fraction in Pregnancy-Associated Thrombotic Microangiopathy: (Results)

Table (10): Comparison of the receiver-operating characteristic (ROC) curves for discrimination between patients with TMA and normal controls using the IPF or schistocyte count

Index	Marker		Difference	z	P-value¶
	IPF	Schistocyte count			
Area under ROC (AUC)	0.820 (0.695 to 0.909)	0.838 (0.716 to 0.922)	0.018 (-0.105 to 0.142)	0.290	0.7722

Diagnostic indices are presented as value (95% CI).

¶DeLong method.

Assessment of Immature Platelet Fraction in Pregnancy-Associated Thrombotic Microangiopathy: (Results)

[figure not shown]

Figure (14): Comparison of the receiver-operating characteristic (ROC) curves for discrimination between patients with TMA and normal controls using the IPF or schistocyte count.

Assessment of Immature Platelet Fraction in Pregnancy-Associated Thrombotic Microangiopathy: (Results)

Table (11): Multivariable binary logistic regression analysis for the relation between the IPF-% and TTP/HUS with adjustment for the confounding effect of the gestational age

Variable	Regression coefficient (B)	SE for B	Wald	P-value	Odds ratio (OR)	95% CI for OR
IPF -%	0.084	0.041	4.105	0.043	1.088	1.003 to 1.179
Gestational age (weeks)	-0.064	0.087	0.539	0.463	0.939	0.792 to 1.112
Constant	-0.271					

Table (12): Multivariable binary logistic regression analysis for the relation between the schistocyte count and TTP/HUS with adjustment for the confounding effect of the gestational age

Variable	Regression coefficient (B)	SE for B	Wald	P-value	Odds ratio (OR)	95% CI for OR
Scistocyte count (%)	0.101	0.052	3.781	0.052	1.107	0.999 to 1.226
Gestational age (weeks)	-0.052	0.088	0.355	0.551	0.949	0.799 to 1.127
Constant	0.420					

Table (13): Correlation between the IPF and schistocytes count in whole study population, patients with TMA, SPE/HELLP, or TTP/HUS, and normal controls

Correlation between IPF-% and schistocyte count			
Group	Number	Spearman rho (ρ)	P-value

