Comparison of the receiver-operating characteristic (ROC) curves between IPF-% or schistocyte count for discrimination between patients with TMA and normal controls revealed no significant difference between IPF and schistocyte count regarding discrimination between patients with TMA and controls ($P > 0.05$) (Table 21), (Figure 28).

Table (21): ROC curves for discrimination between patients with TMA and normal controls using the IPF or schistocyte count

Index	IPF-%	Schistocyte count	Difference	z	P-value¶
Area under ROC (AUC)	0.820 (0.695 to 0.909)	0.838 (0.716 to 0.922)	0.018 (-0.105 to 0.142)	0.290	0.7722

Diagnostic indices are presented as value (95% CI).

¶DeLong method

Assessment of Immature Platelet Fraction in Pregnancy-Associated Thrombotic Microangiopathy: (Results)

[figure not shown]

Figure (28): ROC curves for discrimination between patients with TMA and normal controls using the IPF or schistocyte count.

✚ Correlation between IPF and schistocytes count with different parameters

no significant correlation was found between the IPF-% and schistocytes count in patients with SPE/HELLP, or TTP/HUS, as well as the whole TMA study group (**Figure 29**), (**Table 22**).

Table (22): Correlation between the IPF-% and schistocytes count in whole study population, patients with TMA, SPE/HELLP, or TTP/HUS, and normal controls

	Correlation between IPF % and schistocyte count		
Group	Number	Spearman rho (ρ)	P-value
TMA	37	0.231	0.169

Assessment of Immature Platelet Fraction in Pregnancy-Associated Thrombotic Microangiopathy: (Results)

SPE/HELLP	24	0.190	0.375
TTP/HUS	13	-0.058	0.851

[figure not shown]

Figure (29): Scatter plot showing the correlation between the IPF and schistocyte count in patients with SPE/HELLP or TTP/HUS.

IPF-% and schistocytes counts in TTP/HUS and SPE/HELLP using multivariate analysis

Assessment of Immature Platelet Fraction in Pregnancy-Associated Thrombotic Microangiopathy: (Results)

Multivariable binary logistic regression analysis was used for discrimination between patients with TTP/HUS or SPE/HELLP using the IPF-% and schistocyte count combined. Both IPF-% (odds ratio, 1.11; 95% CI, 1.010 to 1.220; $p=0.031$) and schistocyte count (odds ratio, 1.113; 95% CI, 1.016 to 1.219; $p=0.022$) were independent predictors for TTP/HUS.

Table (23): Multivariable binary logistic regression analysis for discrimination between patients with TTP/HUS or SPE/HELLP using the IPF and schistocyte count combined

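### The marker odds ratios in SAP Tables 11, 12 and 23 appear to be unpenalised logistic estimates from 13 TTP/HUS cases and are expected, on average, to be biased away from 1; Firth refits would reduce this

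*SAP*

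**What the plan says.** The SAP is a results chapter. Its closing section on multivariate analysis says: "Multivariable binary logistic regression analysis was used for discrimination between patients with TTP/HUS or SPE/HELLP using the IPF-% and schistocyte count combined". Table 23 gives B and its SE as "IPF (%) 0.104 0.048" and "Schistocyte count (%) 0.107 0.046". The text repeats the results as effects: "Both IPF-% (odds ratio, 1.11; 95% CI, 1.010 to 1.220" and "schistocyte count (odds ratio, 1.113; 95% CI, 1.016 to 1.219", and describes each marker as independently predictive. Table 24 gives the group sizes behind the combined model: "Positive group (TTP/HUS) 13 (35.1" per cent and "Negative group (SPE/HELLP) 24 (64.9" per cent, 37 patients in all.

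Tables 11 and 12 are two further models with two covariates each. Table 11 concerns the "relation between the IPF-% and TTP/HUS with adjustment for the confounding effect of the gestational age". Table 12 does the same for the schistocyte count. Neither table states its n.

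The protocol's section on statistical methods names SPSS 22 and MedCalc 14 but plans no logistic regression. Neither document names an estimator or mentions penalisation, shrinkage or a caveat about sample size.

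**The concern.** Maximum-likelihood logistic regression is biased in small samples: averaged over repeated studies, the coefficients lie too far from zero. With 13 cases and two covariates, that bias need not be negligible. It is a different matter from optimism in an AUC or a cut-off chosen on the same data, because it acts on the odds ratios themselves. The text offers 1.11 and 1.113 as the effects of the two markers without qualification, so a reader who takes them into a later study would be using estimates with an expected upward bias that a standard method largely removes.

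**Working it through.** **Inputs**
- Cases and non-cases: 13 and 24 (SAP Table 24).
- B and SE, Table 23: IPF-% 0.104 and 0.048; schistocytes 0.107 and 0.046; constant -3.251.
- Table 11: IPF-% 0.084 and 0.041; gestational age -0.064; constant -0.271.
- Table 12: schistocytes 0.101 and 0.052; gestational age -0.052; constant 0.420.
- Medians and quartiles, SPE/HELLP then TTP/HUS: IPF-% 13.0 (9.6-22.9) and 19.5 (15.1-27.7), Table 5; schistocytes 0.5 (0.0-1.2) and 6.5 (0.8-17.6), Table 4.
- Upper tails: not printed, so assumed.

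**Step 1. Reproduce the printed figures.** OR = exp(B); CI = exp(B ± 1.96 × SE); Wald = (B/SE)².
- Table 23 IPF-%: exp(0.104) = 1.110; CI 1.010 to 1.219 (printed 1.010 to 1.220); Wald 4.69 (printed 4.666).
- Table 23 schistocytes: exp(0.107) = 1.113; CI 1.017 to 1.218 (printed 1.016 to 1.219); Wald 5.41 (printed 5.283).
- Table 11 IPF-%: exp(0.084) = 1.088, as printed. Table 12 schistocytes: exp(0.101) = 1.106 (printed 1.107).

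The differences are within the rounding of B and SE. The arithmetic is sound, and the intervals are Wald intervals. That is why ordinary maximum likelihood (ML) is the natural inference.

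**Step 2. Events per covariate.** 13 / 2 = 6.5.

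**Step 3. Sample behind Tables 11 and 12.** If the model is evaluated at average covariate values, the predicted risk should be near the case fraction: 13/37 = 0.351 for the TMA patients, or 13/57 = 0.228 if controls were included. Mean gestational age is (24 × 30.5 + 13 × 29.8)/37 = 30.25 weeks for the 37, and about 28.1 for all 57. Mean markers are assumed: IPF-% about 18 or 14.8, schistocytes about 5.0 or 3.2.
- Table 11, n = 37: -0.271 + 0.084 × 18 - 0.064 × 30.25 = -0.695, risk 0.333. With n = 57 the risk is 0.304.
- Table 12, n = 37: 0.420 + 0.101 × 5.0 - 0.052 × 30.25 = -0.648, risk 0.343. With n = 57 the risk is 0.328.

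Both fit 37 patients better than 57. This is an inference only.

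**Step 4. Size of the bias.** Samples of 37 with exactly 13 cases were simulated, 2,500 to 3,000 per setting. Marker values matched the printed quartiles, and the true coefficients were the printed ones or a reduced version of them. Three Table 23 settings with the truth at the printed B:

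| Assumed maxima: schistocytes SPE/HELLP, TTP/HUS; IPF-% | IPF-% ML mean (truth 0.104) | Schistocytes ML mean (truth 0.107) | Median inflation, IPF-% and schistocytes |
|---|---|---|---|
| 12, 30; 40 | 0.1214 (+16.7%) | 0.1390 (+29.9%) | +7.6%, +12.5% |
| 40, 60; 50 | 0.1273 (+22.4%) | 0.1524 (+42.4%) | +7.2%, +15.2% |
| 60, 60; 45 | 0.1250 (+20.2%) | 0.1607 (+50.2%) | +7.8%, +14.9% |

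Over all settings, the mean inflation was:
- Table 23: +15% to +26% for IPF-% and +21% to +50% for schistocytes.
- Table 11 IPF-%: +12% to +16%.
- Table 12 schistocytes: +27% to +33%.

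Median inflation was about +4% to +18%. The ML estimate exceeded the truth in about 53% to 61% of samples. Firth's mean bias for the markers was about -4% to +8%.

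A separate simulation of 1,500 samples from the Table 23 equation gave ML means of 0.129 (+24%) and 0.143 (+34%), against Firth means of 0.107 (+3%) and 0.111 (+4%). Root mean squared error fell from 0.087 to 0.052 for IPF-% (a drop of 1 - 0.052/0.087 = 40%) and from 0.111 to 0.060 for schistocytes (1 - 0.060/0.111 = 46%).

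**Step 5. What this means for the odds ratios.** On simulated data sets whose ML fit resembled Table 23, Firth odds ratios were about 1.09 (1.084-1.106) for IPF-% and 1.10 (1.085-1.108) for schistocytes. In units of the printed SE, the shifts are (0.104 - ln 1.09)/0.048 = 0.37 and (0.107 - ln 1.10)/0.046 = 0.25.

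**The case against.** A reader might infer that 1.11 and 1.113 are therefore too large. That does not follow. Bias is an average over repeated samples, and a single estimate is above the truth only a little more often than not. This objection stands in full.

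The mean inflation is also pulled up by near-separated samples. The simulated ML errors of 0.087 and 0.111 are 1.8 and 2.4 times the printed SEs of 0.048 and 0.046, so many simulated data sets were less stable than the real one. For schistocytes, the Firth value of 1.10 implies an inflation of 0.107/ln 1.10 - 1 = 12%, well below the mean figures. This too stands, and it is why the percentages are given as wide ranges and the size of the point rests on the odds-ratio scale.

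A second tempting reading is that Table 24 inherits the error. Simulated ML scores were indeed too extreme (median calibration slope 0.82-0.83, against 0.96-0.98 for Firth), but Table 24 prints no predicted probability. Its AUC, sensitivity and specificity depend on rank order. In simulation, ML and Firth scores gave AUCs that differed by 0.002 on average and by at most 0.007 at the 95th percentile, against a printed interval of 0.667 to 0.931. The documents do not support that reading.

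Finally, ML estimates with intervals and an exploratory label would be a defensible report. But the chapter carries no such label, and Firth lowers typical error as well as average bias, so the improvement is more than a matter of taste.

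**Conclusion.** The point holds as a statement about expected bias. With 6.5 events per covariate and apparently unpenalised fits, the marker log-odds in Tables 11, 12 and 23 are expected, on average, to be inflated: by a mean of about 12-50% and a median of about 4-18%. On the odds-ratio scale the likely change in Table 23 is only about 0.01-0.02, well inside the printed intervals.

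The direction is not the same for every coefficient. The gestational-age odds ratios (0.939 and 0.949) would be expected to move up towards 1.

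No change of conclusion is shown. Firth P-values stayed below 0.05 in 85-100% of simulated data sets resembling Table 23. Nothing comparable was computed for Table 11 (P = 0.043, lower limit 1.003) or Table 12 (P = 0.052, lower limit 0.999), which lie closest to the boundary.

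The verdict rests on three assumptions: the estimator is ML, Tables 11 and 12 use the 37 TMA patients, and the unprinted upper tails fall within the range tried. The percentages are simulation results, not figures from the documents.

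**What to change.** Refit Tables 11, 12 and 23 with Firth's penalised likelihood. Report those odds ratios, with penalised profile-likelihood intervals and P-values, in the tables and in the text that now gives 1.11 and 1.113. Name the estimator, state n for Tables 11 and 12, and describe the models as exploratory, since the protocol does not plan them. Rebuilding the Table 24 score from the Firth coefficients is optional, because its rank-based indices would hardly move.

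The cost is three refits on existing data, possibly in a package other than the two named in the protocol, and slightly smaller stated odds ratios for the markers.

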The model had good predictive value as evidenced by increased AUC of 0.827 (95% CI, 0.667 to 0.931). The estimated sensitivity was 92.3% (64.0% - 99.8%), specificity of 62.5% (40.6% - 81.2%), PPV of 57.1%

Assessment of Immature Platelet Fraction in Pregnancy-Associated Thrombotic Microangiopathy: (Results)

(34.0% - 78.2%), and NPV of 93.7% (69.8% - 99.8%). However, no statistically significant difference ($P > 0.05$) was revealed on comparing the AUC value of ROC curve of the combined use of IPF-% and schistocyte counts to AUC values of ROC curves of either marker alone for discrimination between patients with TTP/HUS or SPE/HELLP (Table 25, Figure 31).

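### Table 24 tests the AUC of a fitted score against 0.5 with a standard-normal z, so its P<0.0001 overstates the evidence; a calibrated P is about 0.002-0.005 and still significant

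*SAP*

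**What the plan says.** SAP Table 23 fits a two-predictor logistic model (IPF-% and schistocyte count) to separate TTP/HUS from SPE/HELLP. Table 24 then reports a "ROC curve analysis derived from the predicted probabilities as estimated from the multivariable binary logistic regression model". It lists "Sample size 37", split 13 TTP/HUS and 24 SPE/HELLP, with AUC 0.827 (0.667 to 0.931), "z statistic 4.385" and "P-value <0.0001". The footnote names the DeLong method. The closing text of the SAP adds: "The model had good predictive value as evidenced by increased AUC of 0.827".

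For the same contrast, SAP Tables 7 and 18 give the single markers z=2.028, P=0.043 (IPF) and z=3.022, P=0.003 (schistocytes).

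The Protocol's Statistical methods section mentions neither ROC curves nor logistic regression. Neither document describes a permutation test, resampling, an optimism correction or a validation sample.

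**The concern.** The hypothesis behind the Table 24 P-value is that the combined score does not discriminate, that is, AUC=0.5. Comparing z with the standard normal suits a score fixed before the outcomes were seen. The Table 24 score was not fixed: the logistic fit chose the sign and weight of each marker from the group labels of the same 37 women. Even with useless markers, that choice pushes the apparent AUC above 0.5. The z therefore does not have the distribution it is compared with, and the P-value is too small.

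At stake is how strong the evidence looks. P<0.0001 is the smallest P-value in the TTP/HUS versus SPE/HELLP ROC analysis. Set beside 0.043 and 0.003, it makes the combination look far better established than either marker alone.

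**Working it through.** **Inputs from the SAP.** 13 versus 24 women; AUC 0.827; z=4.385; P<0.0001 (Table 24). Two predictors (Table 23). Spearman correlation between the markers in TMA 0.231 (Table 22).

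**1. Reproduce the printed test.** z=(AUC-0.5)/SE, so SE=0.327/4.385=0.0746. The two-sided normal P for 4.385 is 0.0000116, which agrees with the table. The same form reproduces the single-marker rows: z=2.028 gives 0.043 and z=3.022 gives 0.0025 (printed 0.003). Table 24 is thus the plain test against 0.5.

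**2. Simulate no effect with refitting.** In each data set the 13/24 labels are unrelated to two markers. The logistic model is refitted, and the AUC and DeLong z are computed on the same 37. The documents give no individual data, so the marker distributions are assumptions. Each row has 40,000 data sets.

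| Assumed markers | Mean AUC | P(z>1.96) | P(AUC≥0.827) | P(z≥4.385) |
|---|---|---|---|---|
| Normal, r=0 | 0.624 | 0.180 | 0.0041 | 0.0046 |
| Normal, r=0.23 | 0.623 | 0.178 | 0.0036 | 0.0045 |
| Normal, r=-0.10 | 0.623 | 0.180 | 0.0042 | 0.0045 |
| Normal, r=0.50 | 0.623 | 0.180 | 0.0035 | 0.0042 |
| Skewed with zeros, r=0 | 0.609 | 0.160 | 0.0039 | 0.0050 |
| Skewed with zeros, r about 0.23, lighter tail | 0.614 | 0.169 | 0.0039 | 0.0042 |
| Skewed with zeros, r about 0.23, heavier tail | 0.607 | 0.160 | 0.0035 | 0.0042 |
| Permuted pseudo-data built on the printed quartiles | 0.615 | 0.163 | 0.0036 | 0.0040 |

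Smaller runs (8,000 to 20,000 data sets) gave P(AUC≥0.827) from 0.0021 to 0.0041 and rejection rates from 16.2% to 18.6%. The calibrated P is therefore about 0.002-0.005. The upper tail alone is the right one to use, because the fit has already chosen the direction of each marker.

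**3. Same test, score not fitted.** For a single score fixed in advance (13 versus 24, two-sided): mean AUC 0.500; P(|z|>1.96)=0.066; P(|z|≥4.385)=0.0012 in 40,000 data sets and 0.0008 in a separate 200,000. A direct check agrees. The Mann-Whitney null SE is √[38/(12×13×24)]=0.1007, so z=0.327/0.1007=3.25 and P=0.0012.

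**4. Split the gap.**
- Normal approximation to the DeLong z at this sample size: 0.0000116 becomes 0.0008-0.0012, a factor of about 70 to 100.
- Refitting: 0.0046/0.0012≈3.8 and 0.0042/0.0008≈5.3, a factor of about 4 to 5.

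**5. Calibrate the schistocyte row in the same way.** For an unfitted score, z=3.022 corresponds to about 0.009-0.010, and an AUC of 0.771 to about 0.005-0.007. The combined model gives about 0.004-0.005 by z and 0.002-0.004 by AUC.

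**The case against.** The strongest reply is that little turns on this. The P-value is one table cell and is not repeated in the text. The claim of good predictive value rests on the AUC, not on this P. Both Table 23 coefficients stay below 0.05 (0.031 and 0.022). Table 25 and the closing text already say that the combined AUC does not differ significantly from that of either marker (P=0.117 and 0.435). All of this stands, and it makes the correction minor. It does not make the printed P right.

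Four stronger readings are tempting but not supported:

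- A reader might infer that fitting in the same sample accounts for the whole gap of a few hundred-fold. It does not: a score never fitted to the data already gives about 0.001 (step 3).
- A reader might infer that, once corrected, the combined model is only as well established as schistocytes alone at the printed P=0.003. That corrects one side only. Calibrated alike (step 5), the combined model keeps a somewhat smaller P.
- A reader might infer that the SAP argues from a comparison of these P-values. It does not; it compares AUCs and reports no significant difference.
- A reader might carry 0.002-0.005 over to a likelihood-ratio test. That range belongs to the refitted AUC or z. On pseudo-data matched to the printed summaries, the likelihood-ratio P was mostly lower, about 0.0006-0.0024.

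**Conclusion.** The concern holds as a miscalibrated test and an overstated P-value in Table 24. Under no effect the fitted score averages an AUC of about 0.61-0.62, the nominal 5% test rejects about 16-18% of the time, and the calibrated P is about 0.002-0.005 instead of 0.000012. Most of the tail error comes from the normal approximation; refitting adds 4- to 5-fold on top. For the rejection rate the balance is the other way: the unfitted test is only slightly liberal (about 6%), and refitting causes most of the excess.

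These figures rest on assumed marker distributions. They were stable over normal and skewed shapes and over correlations from -0.10 to 0.50, but the exact P needs the individual data. The combined model stays significant and no conclusion is reversed. P<0.0001 should not be read as stronger evidence than the single-marker P-values unless those are calibrated in the same way (schistocytes alone would be about 0.005-0.010).

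**What to change.** Replace the z and P-value in Table 24 with one of the following:

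- a label-permutation P that refits the logistic model and recomputes the AUC in each permutation (expected about 0.002-0.005). This matches the null directly and is preferable with 37 women;
- the 2-df likelihood-ratio test of the Table 23 model, reported as the overall test, with no expected value set in advance. In null simulations it rejected 6-8% at a nominal 5%, so it is close to nominal but not exact.

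State in the table footnote which test was used. If the P-value is to be read beside the single-marker rows, give those rows permutation P-values too.

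The cost is a short run on existing data or one extra model statistic. The downside is a less extreme P-value. The change concerns the test only: the AUC of 0.827 and its interval remain in-sample figures and would need a separate optimism correction.
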